## Approach

**Overall Strategy:** The primary aim of this application is to investigate relationships of risk factors to the development of PPP at 6 mo following TKR, through independently predictive and mediated models. These risk factors are preoperative thermal pain sensitivity, pain anxiety and catastrophizing; postoperative area of secondary mechanical hyperalgesia or hypoalgesia (numbness) and pain intensity. **PPP** for this study will be defined as "**pain in the operated knee at six months after TKR, with other causes of pain excluded and reported intensity on 0-10 NRS scale of  $\geq 4$ .**" The study will also evaluate the relationship of PPP incidence with the severity of functional impairment. This is a single-site prospective clinical investigation of 300 consented OA patients undergoing primary, unilateral TKR. Although we realize the importance of genetic susceptibility on the development of PPP, the complexity of determining the multiple genes that may contribute to this condition is beyond the scope of this proposal. However, prior to surgery we will obtain a blood sample (8.5 mL) from all patients, process it for DNA analysis, and store at -80° C for future studies by [name], NINR (letter of support) to screen for genetic predictors of PPP, such as COMT and GCH1. We will also obtain three blood samples (5ml each) for RNA analysis. In a previous IRB approved study, we also obtained blood samples for RNA analysis prior to hip replacement surgery and 24 hours afterward and found that IL18R1 was up-regulated while IL-8RB was down-regulated and may be related to the normal acute post

operative inflammation. However, we now need to examine the changes in cytokine gene expression in the TKR patients. All of the blood samples will be sent for analysis to [name] laboratory. The patients' genetic information will stay confidential, and will be identified by a study number, and not a name. This information will not be disclosed to any other third party. Personal data will be stored at Rush University Medical Center. The samples sent to [name] laboratory will be appropriately coded so that the patient's name does not appear on the samples. Data will be kept for 1 year from the time the last patient is enrolled in the study.

Study Calendar	Preop	Post-Incision				Post-operative			
		24h	36h	48h	72h	3 wk	6 wk	3 mo	6 mo
General Physical Examination	X					X	X	X	X
Analgesic Consumption	X	X	X	X	X	X	X	X	X
Knee X-Ray Medical Chart Results	X						X		X
Pain Intensity	X	X	X	X	X	X	X	X	X
Neurophysiologic Assessments	X		X						X
Functional Tests	X		X	X	X	X	X	X	X
Psychosocial tests	X								X

\*ROM will be the only functional test assessed at 36, 48, and 72 hours

**Screening and recruitment feasibility:** A research coordinator/nurse (RN) will screen patients scheduled for Drs. [name] (Co-Investigator), [name], [name], [name] and [name] (participating orthopedic surgeons) to undergo TKR using the criteria detailed below. We will recruit 100 patients/yr. Patient recruitment will be completed within 36 mo; however the 6- mo follow-up extends the study period to a total of 3.5 yrs. If a patient meets study criteria, the RN will contact the patient to obtain verbal consent and assess study eligibility. Selection for inclusion will not be based on race or socioeconomic status.

**Inclusion & exclusion criteria:** *Inclusion Criteria* are: (1) undergoing standard tricompartmental primary TKR; (2) 18- 85 yrs of age; (3) knee to be replaced is the primary source of patient's pain; (4) patient agrees to preoperative and follow-up visits and to comply with the assessment tests; (5) patient consents to standard anesthetic and analgesic protocol, with medical care as deemed necessary by the anesthesiologist, and has no contraindications. (6) Patient has been diagnosed with osteoarthritis. *Exclusion criteria* will include: (1) chronic opioid use  $\geq$  10 mg/day of morphine equivalents within one wk prior to the surgery, and duration of use  $>$  4 wks; (2) history of opioid abuse; (3) inability to understand and communicate with the investigators to complete the study related questionnaires ; (4) patient is planning to undergo another elective joint replacement procedure during the 6-mo period of participation; (5) any co-morbidity which results in severe systemic disease limiting function {as defined by the American Society of Anesthesiology (ASA) physical status classification  $>$  3} (6) taking medication for severe depression .

**Enrollment & Pre-surgery Assessments:** Prior to pre-operative assessments, up to 8 weeks prior to surgery, written informed consent will be obtained. Demographic data such as age, BMI, ASA status and a physical examination will be performed by PI and RN. All of the assessments below will be coordinated by the RN, in conjunction with the routine preoperative laboratory tests for undergoing TKR. We will obtain an 8.5mL DNA blood sample as well as a 5mL RNA blood sample. A knee radiograph (AP and lateral weight bearing views) will also be reviewed by the study's orthopedic surgeon to determine OA severity (scale) and documented. Patients will be instructed to discontinue non-steroidal anti-inflammatory drugs (NSAIDs) a wk prior to surgery as routine clinical practice. A prescription for tramadol hydrochloride 50 mg tablets with a maximum of 3 tablets /day will be provided to the patients to be taken if the pain in the knee is of moderate-to-severe intensity prior to the surgical date.

All measures selected for this study are established, reliable and validated and listed in order of importance. These measures will be classified into Pain, Neurophysiologic Assessment, Psychosocial and Functional test categories and may be used as predictors, mediators, moderators, or outcome measures, depending on specific hypotheses, and will be assessed at various time points as shown in the study calendar.

**(1) Pain Intensity: Numerical Rating Scale (NRS) of pain intensity:** The NRS score has been selected as the primary instrument to quantify pain intensity. Subjects will be presented by the RN with 11-point NRS, (0 = "no pain" and 10 = "worst pain imaginable"), accompanied by the instructions "Please rate your pain by

indicating the number that best describes your pain on average in the past 2h of the affected knee joint." The NRS will be evaluated at rest, and also with movement (patient-initiated flexion). The NRS is used extensively in clinical trials reported in the orthopedics, pain and surgical literature. Within the pain literature, a NRS <4 is considered mild pain, while a NRS ≥4 is moderate-to-severe pain.

**(2) Neurophysiologic Assessment:** The following neurophysiologic assessments will be performed at the Department of Anesthesiology Clinical Research Section (Room 1487 Jelke), where the PI or Co-PI ([name]) will supervise the RN in the performance of these tests. These assessments have been performed by the PI and [name] (Co-investigator) for other clinical and basic research respectively.

**(a) Thermal pain stimulation:** Prior to surgery, a heat probe (3x3 cm; TSAll instrument; Medoc®) will be applied 16 cm above the center of the patella as a measure for **thermal pain sensitivity**. Probe temperature will be ramped up from 32° C at a rate of 4°C/sec until 47 °C is reached, and then maintained for 5 sec. After the 5 sec period, subjects will rate pain intensity (0-10 NRS scale). If subject requests removal of probe before 5 sec period due to intolerable discomfort, it will be removed and a maximal value of 10 will be given. The test will be repeated 4 times and the average of the responses will be calculated. This procedure will be repeated on the contralateral leg. **(b) Examination of the knee for peripheral neuropathic pain (StEP)** using the following 9 parameters and calculating a score to determine the presence of neuropathic pain (total score ≥ 4). The StEP will detail the symptoms and signs of the pain in the knee. This test will be performed 5 cm medial and 5 cm rostral to the center of the patella on the un-operated knee as a control and then the operated knee.

- Sympathetic: Recording of skin characteristics (yes/no evaluation of color, sweating, trophic changes)
- Tactile allodynia (touch): Numbness, allodynia or hyperalgesia to von Frey filament stimulation, with corresponding NRS pain intensity
- Tactile hyperalgesia (blunt pressure): Decreased or increased response, with corresponding NRS pain intensity
- Dynamic tactile allodynia (brush movement): Decreased or increased response, with corresponding NRS pain intensity
- Vibration sense (tuning fork): yes/no to decreased response to stimulation at the tibia bone ventral midline, 15 cm below lower point of proposed incision
- Evoked pain (pinprick): decreased or increased response, with corresponding NRS pain intensity
- Non-painful warm stimulus (TSAll instrument, Medoc®): decreased or increased response, with corresponding NRS pain intensity
- Non-painful cold stimulus (TSAll instrument, Medoc®): decreased or increased response, with corresponding NRS pain intensity
- Mechanical temporal summation: yes/no to increased pain with repetitive von Frey stimulation.

**(3) Psychosocial measures:** These measures will be supervised by the PI and administered by the RN.

**(a) Pain Catastrophizing Scale (PCS):** The PCS will be used to measure catastrophizing. The 13-item measure asks respondents to rate, using a 5-point Likert scale ranging from 0 (*not at all*) to 4 (*all the time*), the degree to which they have certain thoughts and feelings when experiencing pain. Higher scores indicate greater use of catastrophic thinking. The PCS has exhibited strong internal consistency ( $\alpha=0.93$ ), concurrent and discriminant validity, and high test-retest reliability over a 6 wk period ( $r = 0.78$ ). Research suggests that the PCS is responsive to treatment (measure is in public domain-no permission required for study).

**(b) Beck Depression Inventory (BDI-II):** The BDI-II assesses emotional function by measuring the level of depressed mood based on attitudes and symptoms that are common among depressed subjects and uncommon among those not depressed. BDI-II, which has been widely used in pain studies, consists of a 21-item self-report measure of depressive symptoms experienced during the past wk. BDI-II is an update with modifications made to conform scoring to diagnosis as defined by the DSM-IV (permission obtained for study).

**(c) State-Trait Anxiety Inventory (STAI):** STAI has two variations, STAI-state and STAI-trait, and each is a 20-item self-report assessment device, one for state anxiety and one for trait anxiety. The state anxiety score reflects a transient evaluation of anxiety and in particular the current self-report state. Trait anxiety measures a subject's dominant response style although modification can be seen with psychological interventions (permission obtained for study).

**(4) Functional measures:** Measures of the study will be supervised by the PI and administered by RN.

(a) *Knee range of motion (ROM):* The degree of active (patient moving the knee) and passive (movement of the knee with the aid of RN) knee flexion, will be measured using a goniometer. The PI has previously performed ROM measures with the aid of physical therapists.

(b) *Western Ontario and McMaster Universities Osteoarthritis Index (WOMAC):* A widely used measure of symptoms and physical disability specifically designed for patients with OA of the lower extremity. This instrument evaluates 3 dimensions: pain, stiffness and physical functional disability (permission obtained).

(c) *SF-36 (SF-36):* A self-report survey containing 36 items and is the most commonly used measure of physical functioning. The SF-36 is a general measure of health status as opposed to one that targets specific population. Accordingly, the SF-36 can provide a benchmark with which to compare specific populations. It has well described properties and sensitivity (permission obtained for current study use).

**(5) Skin Temperature:** Skin temperature, the abnormalities of which have been associated with neuropathic pain conditions, will be measured medial and lateral to the center of the patella on the operated knee, and on the contralateral knee, as is standard at the Rush Pain Center.

**Day of surgery:** Patients will not receive oral adjuvant analgesics preoperatively on the day of surgery. The method of anesthesia for the case will be that which is deemed appropriate by the attending anesthesiologist. For patients receiving general anesthesia, standard anesthesiology practice will be followed. In the case of patients receiving epidural anesthesia, on the morning of surgery, patients will be sedated with midazolam (0.05 mg/kg titrated to effect) and an epidural catheter at the L3-L4 or L4-L5 vertebral level. This procedure will be carried out in the designated regional room with the patient in sitting position. The skin will be infiltrated with lidocaine and using an 18G Touhy needle®, the epidural space will be identified via the loss of resistance technique with air and glass syringe. A 20G catheter will then be threaded 3-5 cm in the epidural space and a test dose with 1.5% lidocaine and epinephrine will be performed. The PI will place all the epidural catheters for consented study patients, to minimize variability.

The standard ASA monitors will be placed. Written standard instructions will be given to the anesthesiologist assigned to provide intraoperative care of these patients, who will be one of the members of the orthopedic anesthesia section, of which the PI is the director. Epidural anesthesia will be induced with titration of 2.0% lidocaine (10-20 mL) with epinephrine (1:200,000). Prior to commencing surgery, a dermatomal sensory and motor level will be obtained. Patients will be sedated with propofol titrated to effect at a rate of 20-50 µg/kg/min. They will be maintained normothermic with fluid warmer and active heating devices. In addition, hemodynamic parameters will be titrated to maintain mean blood pressure within 20-30% of baseline hemodynamic status (and not below 60 mmHg mean blood pressure). All intraoperative variables such as heart rate, blood pressure, O2 saturation and temperature, intraoperative local anesthetics, sedative drugs used, amount of fluid given, blood loss, duration of surgery and tourniquet time will be documented. Once the surgery is completed, patients will be transported to the recovery room.

**Standard TKR:** Skin incision will be considered time zero; and the length of incision will be recorded. TKR will be performed under tourniquet control, using an abbreviated medial parapatellar approach with the arthrotomy extending into the quadriceps tendon for 2-4 cm above the superior pole of the patella, and without patellar eversion. A primary, cruciate retaining tricompartmental TKR will be performed in all cases (NexGen CR, Zimmer, Warsaw, IN®); all components will be cemented and the patella will be resurfaced. No local anesthetic will be infiltrated at closure of the surgical wound. The knee will be closed in 90 deg of flexion over a drain. Any intraoperative complications, especially nerve trauma, will be recorded.

**Post-Incision to Hospital Stay:** *Acute postoperative pain management:* For patient's that received general anesthesia, standard post-operative analgesic practice will be followed. For patients with epidural catheters in place, an epidural infusion of bupivacaine (0.1%) and fentanyl (5 µg/ml) will be started upon entry to the recovery room, using a continuous basal infusion at 6 mL/h with superimposed patient-controlled epidural analgesia (PCEA) bolus dose of 1 mL every 15 min, with a 4 h lockout of 40 mL to be delivered by the infusion pump. Patients will be instructed prior to surgery, on PCEA operation (routine clinical practice) by the acute-pain service nurses, who report to the PI. If the patient complains of severe pain, the acute pain nurse will be

contacted and the epidural infusion titrated (per previous published protocol). However, if these measures fail and the patient has severe pain, intravenous opioids (morphine 2 mg bolus) will be administered. Records will be kept of the total amount of epidural solution consumed, including morphine boluses, in increments of 4h for the 24h postoperative period. After 24 hours, the epidural catheter will be removed. We customarily administer warfarin (oral 5 mg) for deep venous thrombosis prophylaxis on the night of TKR. An International Normalized Ratio will be obtained prior to removing the catheter. Once the epidural catheter is removed, all patients will receive hydrocodone 10 mg/acetaminophen 325 mg, 1-2 tablets every 4-6h depending on the NRS pain score for a maximum of 6 tablets/ day (to keep within current geriatric guidelines <3.25 mg/day acetaminophen), until discharged from the hospital. Patients having NRS  $\geq 4$  for more than 1h will receive intravenous morphine 2-4 mg as needed every 15 min for a maximum of 15 mg over a period of 2h. Patients allergic to intravenous morphine or oral hydrocodone will receive an equivalent dose of intravenous hydromorphone or oral oxycodone respectively. All analgesics administered over 0-72h will be recorded in the data collection book for inclusion as covariates in analyses. Although a more complex algorithm for pain management, including multimodal non-opioid analgesia, could be used and continued for at least 2 wks later, those analgesics might become factors themselves that influence the development of PPP, and therefore will not be used in this proposed study. We will also obtain a 5mL blood sample for RNA analysis during the hospital stay (when wound inflammation is maximum).

[figure not shown]
**Postoperative Management:** Routine vital signs will be recorded on the floor and transferred to the data collection book. The patients will undergo routine physical therapy sessions twice/daily until they meet the hospital discharge criteria as determined by the therapist.

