#### **Long-term Assessments (same methods used pre-surgery):**

(1) **Pain Intensity:** NRS of the operated knee will be obtained by RN from the patients at the 3 wk, 6 wk, 3 mo and 6 mo scheduled visits.

(2) **Neurophysiologic Assessment** will be performed at the 6 mo scheduled visit.

(a) *Examination of the knee for peripheral neuropathic pain (StEP)*

(3) **Psychosocial Measures:** Beck Depression Inventory will be administered at 6 mo by RN.

(4) **Functional Measures:** ROM, WOMAC and SF-36 questionnaires will be administered at 3 wk, 6 wk, 3 mo and 6 mo.

(5) **Skin Temperature:** Skin temperature will be performed at 6 months

**Patients who have NRS $\geq$ 4 at three wks and beyond:** For patients having NRS $\geq$ 4 at 3 wk and beyond, the oral opioid regime will be continued. If the hydrocodone/acetaminophen regime does not maintain a NRS $<$ 4, then oral long-acting opioids such as time-release oxycodone 10 mg twice/day will be prescribed. The purpose of closely following the analgesics and NRS for the study patients is to ensure that at the 6-mo time point the analgesic consumption is within a standard protocol for all patients, whether they do or do not have PPP. Patients who have persistent pain at the 3 and 6-mo visits will be evaluated by the orthopedic surgeon for prosthetic-related failure. An examination will be performed to evaluate instability of the tibial femoral joint or patellar maltracking. Plain radiographs will be reviewed by the orthopedic surgeons (Co-investigators) for evidence of prosthetic loosening, malposition and patellar maltracking, as well as overall axial alignment to ensure coronal alignment is within the range of neutral to 10 deg of valgus. If this evaluation is negative, an erythrocyte sedimentation rate (ESR) and C-reactive protein (CRP) measurement will be obtained as a screening tool for infection. If these indices are abnormal (ESR $>$ 30 mm/h; CRP $>$ 10 $\mu$ g/mL), an aspiration of the knee will be performed, including a synovial fluid white blood cell count with differential and culture to rule

out infection. These parameters are based on previous work by [name] (Co-investigator) in this specific topic.

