**General statistical analysis:** Descriptive statistics will be reported as mean and standard deviation (SD) for continuous normally-distributed variables, and reported as counts and percentages for dichotomous variables. Assumptions will be evaluated and, if violated, either corrective measures will be taken (data-transformation) or other less restrictive methods will be implemented. Error inflation for multiple pre-planned comparisons will be corrected by using the Bonferroni step-down method. Models will be examined with no risk factors, with individual risk factors, and with multiple risk factors. The distribution of the primary outcome, NRS pain scores at 6 mo, will be evaluated, transformed to normal and then modeled as a continuous variable. If this is not possible, *then the dichotomous version*, as defined for PPP, will be used. We expect that the primary outcome of PPP (dichotomous) will be modeled using a logistic regression because the distribution of NRS pain scores from our preliminary survey data was strongly bi-modal (modes:0, 3). Thus it appears that this kind of distribution represents two distinct populations (a normally distributed pain population and a unimodal 'no-pain' population). Pain intensity (continuous) will be separately modeled for those patients who report a non-zero pain level. Risk factors will be evaluated, for **independent** association with the outcome variable, first for linearity and then for model fit using backward stepwise logistic regression (criterion  $P<0.05$ ). Model fit will be assessed by the Hosmer-Lemeshow test and validity of the fit models and predictive accuracy will be assessed using bootstrapping methods as well as the AUC 'c-index'. Analysis will also be performed on the raw NRS score (at 6 mo) using general linear models and mixed model regression as this may elucidate additional details about relationships among the factors and how they relate to pain at 6 mo. **Mediation** models will be evaluated based on techniques pioneered by Baron and Kenny, but with the modification of bootstrapping techniques to produce multiple mediator results with confidence intervals. Sobel method and  $R^2$  effect-size measures will be used to test and evaluate the mediation effects as well. Distributional assumptions and

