**Covariates:** Preoperative covariates included are as follows: age, weight/BMI, OA severity and ASA status. Perioperative covariates include: postoperative analgesic consumption and duration of surgery. Complications after TKR will be recorded and included as a summed incidence. Patient questionnaires of drug use in the first three wks postoperatively will be converted to daily morphine equivalents and included as a covariate in the predictive models. Although the protocol stipulates uniformity in medication use during the acute postoperative period, once the patient leaves the hospital, their analgesic use over the next 6 mo cannot be rigidly controlled. To reduce variation we will prescribe analgesics as needed (per protocol above mentioned) and will remain in contact with the patients to record additional medication.

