#### Potential Difficulties and Limitations

1. We have no way of directly assessing minor nerve damage following TKR.
2. Patient may decide to undergo another elective joint replacement procedure during the 6-mo postop period
3. Although power analysis is based on 17.8% PPP incidence, TKR procedures may vary over the 3-yr duration of study. However our power estimates are conservative and our multivariate analyses are robust and powerful.
4. 6 mo assessment of PPP can be complicated by opioid use in some patients. However, this factor is considered as a covariate in the analysis.

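### Surgeon is in no planned model, although five surgeons operate; this can bias the links from acute pain and hyperalgesia area to persistent pain if surgeons affect both ends of the link

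*Combined protocol and SAP*

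**What the plan says.** Screening and recruitment feasibility names five surgeons at one site whose patients are screened, described as "participating orthopedic surgeons) to undergo TKR using the criteria detailed below".

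The Covariates paragraph gives the adjustment set: "Preoperative covariates included are as follows: age, weight/BMI, OA severity and ASA status". It continues: "Perioperative covariates include: postoperative analgesic consumption and duration of surgery". It then adds: "Complications after TKR will be recorded and included as a summed incidence". Surgeon is not listed. The example equation under The prediction equation contains age, preoperative pain sensitivity, hyperalgesia, postoperative NRS, trait anxiety and catastrophizing, and again no surgeon. General statistical analysis mentions "general linear models and mixed model regression", but for the raw 6-month NRS score, and it names no surgeon effect.

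The plan does limit surgical variation. Under Standard TKR: "A primary, cruciate retaining tricompartmental TKR will be performed in all cases". Approach, implant, cementing and patellar resurfacing are common to all. Incision length, blood loss and tourniquet time are recorded but are not listed covariates.

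The PPP definition (Overall Strategy) requires other causes of pain to be excluded. Patients with persistent pain at 3 and 6 months "will be evaluated by the orthopedic surgeon for prosthetic-related failure".

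**The concern.** The protocol itself treats surgery as a source of variation in both predictor and outcome. The Significance section counts surgical variables among the suspected risk factors for PPP, and it says that surgical trauma produces the hyperalgesia that serves as the mediator in Hypothesis 2. Two routes from surgeon to PPP need not pass through measured acute pain or area. One is minor nerve damage, which Potential Difficulties and Limitations (item 1) says cannot be assessed directly. The other is the orthopedic judgement on whether pain has another cause.

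If surgeons who leave larger areas of hyperalgesia also produce more PPP by one of these routes, part of the area-to-PPP association is a difference between surgeons. This matters most for Hypothesis 2, because the protocol reads the mediation result as a causal mechanism and a target for intervention. It matters less for pure prediction.

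The plan takes care over provider variation elsewhere: under Day of surgery, the principal investigator places all epidural catheters to limit variability. Nothing comparable is done in the analysis for the operator.

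**Working it through.** The plan gives no figure for variation between surgeons, so there is none to reproduce. The check asks how much omission could matter over a stated range of assumptions.

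**Inputs from the documents** (Power analysis and sample size calculation)
- PPP incidence: 46/259 = 17.8%.
- Completers: 300 × (1 − 0.15) = 255. Expected cases: 255 × 0.178 = 45.4.
- Assumed effect of acute pain: OR 1.24 per NRS point, SD 2.9. Per SD: 2.9 × ln 1.24 = 0.62, so OR = e^0.62 ≈ 1.87.

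**Assumptions (not in the documents)**
- Five surgeons with equal numbers: 255/5 = 51 patients each.
- Surgeon SD on the logit scale of 0.3 to 0.7. With logit(0.178) = −1.53, an SD of 0.5 means logits of −2.03 and −1.03 one SD either side, that is PPP of 12% and 26%.
- 5 to 10% of predictor variance lies between surgeons.
- Correlation between a surgeon's effect on the predictor and on PPP: 0 to 0.8.

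**Expected bias.** For a standardised predictor with no effect of its own, the average bias in its log-OR when surgeon is left out is roughly

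bias ≈ (4/5) × correlation × surgeon SD × √(between-surgeon share),

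where 4/5 arises because the intercept absorbs the mean of the five surgeons.
- SD 0.3, 5%, 0.8: 0.8 × 0.8 × 0.3 × 0.224 = 0.04
- SD 0.5, 10%, 0.8: 0.8 × 0.8 × 0.5 × 0.316 = 0.10
- SD 0.7, 10%, 0.8: 0.8 × 0.8 × 0.7 × 0.316 = 0.14

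At correlation 0 the average bias is zero.

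**Simulation.** 255 patients, a predictor with no effect, and logistic models with and without four surgeon indicators, two-sided 5% test, 2,500 to 4,000 simulated studies per setting. Ranges are over repeat runs. The Monte Carlo standard error at 5% with 2,500 runs is √(0.05 × 0.95/2500) = 0.44 percentage points.

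| Surgeon SD | Share of predictor variance | Correlation | False positives, surgeon omitted | Surgeon included | Log-OR bias per SD, omitted |
|---|---|---|---|---|---|
| 0.3 | 5% | 0 | about 5% | about 5% | none |
| 0.7 | 10% | 0 | 8 to 9% | about 5% | none on average |
| 0.3 | 5% | 0.8 | about 6% | about 5% | 0.04 to 0.05 |
| 0.5 | 10% | 0.8 | 10 to 12% | about 5% | 0.10 |
| 0.7 | 10% | 0.8 | 15 to 17% | about 5% | 0.12 to 0.13 |

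At correlation 0.3, with SD 0.3 to 0.5 and a 5 to 10% share, false positives are about 5 to 8% and the bias is 0.01 to 0.04.

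Against the planned effect of 0.62 per SD, a bias of 0.10 is 0.10/0.62 = 16% and a bias of 0.13 is 21%. On the NRS scale, 0.10/2.9 = 0.034 per point, so a null predictor would show an OR of about 1.03. With a true OR of 1.24, a correlation of 0.5 to 1, SD 0.5 and a 5 to 10% share, the estimate without surgeon is 1.25 to 1.29 per point.

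**Cost of adjusting.** With no surgeon differences and no other covariates, power at OR 1.87 per SD is 96.7% without surgeon and 96.4% with it. With twelve other covariates and R² of 0.5, the two models give 73% and 74%, which is no visible difference. Events per parameter in the six-predictor example equation would fall from 45.4/6 = 7.6 to 45.4/10 = 4.5.

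**The case against.** A good deal of the opposing case stands.

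- **Existing control.** One approach and one implant are used for every patient, and summed complications are adjusted for alongside duration of surgery. Surgery is not left uncontrolled.
- **Causal path.** Trauma that raises PPP only through acute pain or hyperalgesia is the hypothesised mechanism, not confounding. Bias needs a second route from the same surgeons to PPP.
- **Outcome judgement.** The research nurse obtains the NRS. Exclusion of other causes follows partly set criteria: an alignment range, ESR and CRP cut-offs, then aspiration. Radiographs are reviewed by surgeons labelled co-investigators, and the recruitment list labels only one of the five that way. A reader might infer that each patient's own surgeon decides the endpoint; the documents do not show it. Differences in judging would mainly misclassify PPP, and they bias a predictor only if linked to surgeon-level pain or area.
- **Procedures varying.** The statement that "TKR procedures may vary over the 3-yr duration of study" might be read as admitting differences between surgeons. It concerns drift over time and its effect on incidence and power.
- **Preoperative predictors.** Thermal sensitivity, anxiety, catastrophizing and age are fixed before surgery, so surgical trauma cannot shift them. The documents give no reason to force surgeon into models for these alone, or into Hypothesis 4.
- **Form of adjustment.** Five clusters are too few for a dependable random intercept. A conditional logistic model gives no intercept, hence no predicted probability for the prediction equation.

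What does not stand is the view that unrelated surgeon effects are harmless. The average bias over many possible sets of surgeons is zero, but this study has one set of five whose effects can align by chance. That is why false positives reach 8 to 9% in the stronger unrelated setting.

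**Conclusion.** The omission is real: five surgeons, and surgeon in no listed covariate set or specified model. Its consequence is conditional. A reader might infer that differences between surgeons are in fact being credited to acute pain and hyperalgesia. The documents do not support that, because they give no between-surgeon variance, no surgeon volumes and no evidence that surgeon effects on predictor and outcome are linked.

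What can be said is that the area-to-PPP path of Hypothesis 2 and the postoperative predictors of Hypothesis 1 are open to this bias. It is negligible at the weak end of the assumed range. At the strong end it roughly triples the false-positive rate, and the upper figures depend on an assumed correlation of 0.8. Since adjustment restores the 5% level at every setting tried and costs little power, the change is worth making for those models.

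**What to change.** 1. In Covariates, add operating surgeon as a recorded variable.
2. In the Hypothesis 2 models, include surgeon as fixed indicators in both the area equation and the PPP equation. As ordinary covariates, these need no random effect or stratified likelihood in the mediation macro.
3. In the Hypothesis 1 models for postoperative pain and hyperalgesia area, include the same indicators and exempt them from backward elimination at P<0.05.
4. At minimum, prespecify items 2 and 3 as a sensitivity analysis reported beside the result without surgeon.
5. Leave the prediction equation without surgeon terms, since an intercept for one of these five surgeons is of no use elsewhere.

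The change is to SAP wording, because each patient's surgeon is already known. The cost is four degrees of freedom with about 45 PPP cases. With equal volumes each surgeon would contribute about 51 × 0.178 = 9 cases, but volumes are not stated and a surgeon with few patients could give a sparse stratum. The SAP should say in advance how such a stratum will be handled, for example by pooling surgeons below a stated number of patients.
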